8.1. Adverse Experiences

The investigator will closely monitor subjects for evidence of adverse events. All adverse events will be reported and followed until satisfactory resolution. The description of the adverse experience will include the time of onset, duration, intensity, etiology, relationship to the study drug (none, unlikely, possible, probable, highly probable), and any treatment required.

8.2. Premature Discontinuation

If a subject withdraws from the study, the subject will be replaced to provide the required number of subjects. Subjects will be withdrawn if the investigator decides that discontinuation is in the best interest of the subject, or the subject requests withdrawal from the study.

9. Data and Safety Monitoring Plan

Studies conducted in the Departments of Pediatrics, Otolaryngology, and Anesthesiology follow the Washington University Institutional Review Board Policies and Procedures (last revision April 20, 2015). All individuals working on the study are required to read and be familiar with and compliant with the IRB Policies and Procedures. The specific monitoring plan for this investigation is commensurate with the risks and the size and complexity of the investigations planned. The potential risks are attributable to performing unattended polysomnography. Based on the small size and relatively low risk nature of the protocol, the investigating physicians are involved in the monitoring plan. A full DSMB is not needed. These individuals will review the annual summary of adverse events. In addition, they will review all reports of a Serious Adverse Event, or an Unexpected Adverse Event. The investigators will follow the requirements for principle investigator reporting requirements as outlined in Section X of the IRB Policies and Procedures.

References:

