2. Enrollment: Patients and their families who present to the Washington University Department of Pediatric Otolaryngology with a suspected diagnosis of sleep disordered breathing will be given information regarding the study in the otolaryngologist's office. A member of the research team will approach the patient and their family once they are identified as needing an in-laboratory sleep study as part of their work up for sleep disordered breathing. Written informed consent will be obtained from the patient's family and assent will be obtained from the patient at that time. The study group will consist of one hundred patients who require diagnostic PSG for sleep disordered breathing. Inclusion and exclusion criteria are based on independent risk factors for respiratory complications following tonsillectomy and adenoidectomy ⁷. The Washington University Pediatric Otolaryngology clinic sees approximately 100 patients a month with tonsillar hypertrophy, snoring, or other concerns for sleep disordered breathing that would warrant a sleep study; the St. Louis Children's Hospital Sleep Laboratory performs approximately 1300 Type I sleep studies a year. We plan to enroll 125 patients in this study, assuming a 20% drop out rate from the study, with an end goal of one hundred study patients. Given the frequency with which patients present with concern for sleep disordered breathing this should be accomplishable in the planned time frame.

3. Eligibility:

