4.1. Study design: Single-center, un-blinded, feasibility, and methods comparison study

4.2. Otolaryngology Clinic Assessment: Subjects will be identified from patients presenting to the Washington University in St. Louis Pediatric Otolaryngology Clinic who are suspected of having sleep disordered breathing. Subjects who are identified by an attending otolaryngologist as requiring polysomnography as part of their work up will then be approached by a member of the research team who will explain the study to the subject and their family and obtain informed consent. During this visit, subjects will also be administered a short, validated sleep questionnaire, the Modified STOP-Bang Tool for Stratifying OSA Risk in Adolescent Children ⁹. This questionnaire is 8 questions and routinely administered in the Washington University Pediatric Otolaryngology offices.

4.3.1. Unattended Polysomnography: All eligible subjects will be asked to conduct an unattended, overnight sleep study performed in their home prior to in-laboratory polysomnography, using a standard Type III portable monitor. This study will be performed with

an FDA approved sleep monitor (e.g CleveMed SleepView or similar). Per American Academy of Sleep Medicine (AASM) guidelines, portable sleep monitoring will include air flow, respiratory effort, heart rate and blood oxygenation. Airflow will be measured using a nasal cannula and pressure transducer which is located within the home sleep test (HST) recording device. Respiratory effort will be recorded using Respiratory Inductance Plethysmography (RIP) belts that will go around the chest at the nipple line and around the abdomen at the navel level. Blood oxygenation and heart rate will be recorded by pulse oximetry that will be placed on one finger. Each study participant and their family will be shown and educated on how to apply each of the sensors by a member of the study team. Unattended sleep studies will be interpreted by an individual trained in sleep medicine. The first assessment of the Unattended sleep study for each individual patient will be readability of the recordings.

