Polysomnography testing will determine the apnea hypopnea index (AHI), blood saturation oxygen nadir (SPO₂ nadir), and average blood oxygen saturation ³. The AHI is defined as the average number of hypopneas (episodes of decreased breathing) and apneas (episodes of cessation of breathing) per hour of sleep. Apneas and hypopneas will be defined per the American Academy of Sleep Medicine manual for scoring sleep and associated events ¹⁰. The objective is to obtain greater than or equal to 6 hours of data adequate for polysomnography analysis and determination of an apnea hypopnea index (AHI), average SPO₂, and SPO₂ nadir using home un-attended polysomnography.

A McGill Oximetry Score ¹¹, which only uses the frequency and depth of SPO₂ desaturations throughout a night's sleep to assign a score of 1 (normal/inconclusive), 2 (mildly abnormal), 3 (markedly abnormal), and 4 (severely abnormal) will be also be assigned to each home sleep test.

Fidelity of data collection using at home sleep studies is reliable, but not 100% reliable ³. For example, subjects may unconsciously remove the nasal cannula or the finger pulse oximeter in their sleep, resulting in data drop outs. A subject's parent or guardian will be requested to periodically monitor the subject throughout the night and be instructed on how to reapply sensors to minimize data drop outs. Should data from an initial sleep study be uninterpretable based on sleep study expert opinion we will ask the subjects to attempt the unattended sleep study an additional time. A recent study on the feasibility of Type II comprehensive (i.e. greater than 7 channel) pediatric sleep studies, reported that 91% of home sleep studies are successful on initial attempt and a total of 98% are successful after one repeat testing ¹². A 2013 assessment of Type III sleep studies performed both in a hospital setting (26 patients) and at home (75 patients) found that technically acceptable and interpretable studies were obtained from 93% of subjects ¹³.

Should data from the second sleep study be uninterpretable we will not proceed with further testing of these subjects by home sleep study. Regardless of whether a subject successful completes home sleep testing, in-laboratory polysomnography will still be performed as part of their work up for sleep disordered breathing.

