Per American Academy of Sleep Medicine (AASM) guidelines, in-laboratory sleep monitoring is attended by a specially trained technologist who sets up the sleep study, observes the subject throughout the duration of the sleep study, and is available to troubleshoot in real time any monitoring issues that may arise. In-laboratory polysomnography consists of 21 leads that measure electroencephalogram, electrocardiogram, air flow, respiratory effort, heart rate, activity, and blood oxygenation monitoring. In-laboratory sleep studies are scored by a trained Registered Polysomnographic Technologist or Registered Sleep Technologist and interpreted by a physician. Polysomnography testing will determine the sleep stages, apnea hypopnea index (AHI), blood saturation oxygen nadir (SPO₂ nadir), and average blood oxygen saturation, as defined above ³. A McGill Oximetry Score will also be calculated for the in-laboratory PSG.

4.6. Subject assessments: The unattended home polysomnogram will record blood oxygen concentration, pulse rate, respiratory effort, air flow and respiratory effort. The in-laboratory polysomnogram will record these parameters and will also measure electroencephalography, electrocardiogram, and heart rate.

4.7. Conclusion of study: The study ends with the completion of the in-laboratory polysomnogram. Additionally, the study ends at any time the patient or parent/caregiver requests it to end. Appropriate treatment for any diagnosis of sleep disordered breathing will proceed based on the attending otolaryngologist recommendations. Recommendations and treatment will not be affected by participation in the investigation. As home sleep testing in pediatric patients is exploratory; only the in-laboratory sleep study will be used in making any diagnosis of sleep disordered breathing and in determining treatment options.

5. Data Collection and Monitoring

5.1. Clinical Assessments: At the completion of both the unattended and in-laboratory polysomnography we will determine an Apnea-Hypopnea Index, Average SPO₂, and SPO₂ nadir for each subject. An assessment of the technical quality of each study will be made. The in-laboratory polysomnogram will be scored and interpreted via standard practice for the St. Louis Children's Hospital Pediatric Sleep Center and included in the patient's medical record. The unattended polysomnogram will not be included in the patient's medical record and will only be accessible to study team members.

6. Outcome Measures

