6.2. Secondary Outcome Measures

6.2.1. Comparison of AHI between unattended and in-laboratory polysomnography
6.2.2. Comparison of average SPO₂ between unattended and in-laboratory polysomnography

6.2.3. Comparison of SPO₂ nadir between unattended and in-laboratory polysomnography

6.2.4. Comparison of sleep disordered breathing diagnosis between unattended and in-laboratory polysomnography

6.3. Exploratory Outcomes Measure: Comparison of McGill Oximetry Scores between unattended and in-laboratory polysomnography.

6.4. Analysis: The primary outcome is the feasibility of obtaining an adequate sleep study from unattended polysomnography in pediatric patients. Percentages of studies that have 6 hours of data sufficient for analysis will be reported. The study will be defined feasible if 85% or more of participants provide 6 or more hours of analyzable data. Descriptive statistics will be used to describe the AHI, SPO₂ nadir, SPO₂ average, and diagnosis obtained using each method. Continuous secondary outcome measures will be compared using paired-t tests or its non-parametric equivalent Wilcoxon signed rank test. The Friedman test will be used to compare ordinal outcome measures. Agreement between home sleep testing and in-laboratory PSGs will also be compared using Bland-Altman Analysis ¹⁴. A General Linear Model Approach will be used to explore the role of potential confounders including age, sex, weight, and race differences when performing analyses. If our hypothesis is correct, home sleep studies will be feasible in our study population.

7. Potential Risks

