CONFIDENTIAL: This document is the intellectual property of [name], [name], and [name], PhD. Acceptance of this document constitutes the agreement by the recipient that no unpublished information contained herein will be published or disclosed without prior written approval.

Inclusion and exclusion criteria, monitoring, and the clinical protocol are designed to ensure that risks are absolutely minimal. Subjects and their families are informed that participation is voluntary and they may refuse to participate and may withdraw from the study at any time without penalty. Subjects will be told that in the unlikely event of a physical injury as the direct result of study procedures, they will be cared for by a member of the investigating team at no cost, within the limits of the Washington University compensation plan.

During the unattended sleep study, there is minimal risk. Subjects will be in their own home and should the unattended sleep study equipment prove too much of a discomfort or too challenging for parents to maintain they will be free to remove the device at any time. A specific monitoring plan to minimize the possibility that the device could present a choking hazard is described above. In-laboratory, attended polysomnography is standard of care and as such carries minimal risk.

Regarding confidentiality; 1) all subjects will be assigned a study ID number, and 2) unattended polysomnography reports will be kept confidentially. They will be coded, with information linking code numbers to names kept at a separate location, under lock and key. 3) The link to identifiers will be destroyed at the end of the study. 4) Data will be stored under lock and key (office, file cabinet) and only the investigators and research team will have access. If data are published, there will be no link to identifiers. Study data will not be revealed to any organization, individuals other than the subjects, or the subjects themselves. 5) Study data from the unattended polysomnography will not be entered in subjects' medical records.

8. Management of Intercurrent Events

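### Replacing every withdrawn child to reach 100, with no statement that withdrawn children stay in the 85% count, could let the feasibility verdict describe children who stayed instead of children given the monitor

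*Protocol*

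**What the plan says.** Three parts of the protocol bear on this point.

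- **Replacement (8.2).** "If a subject withdraws from the study, the subject will be replaced to provide the required number of subjects". Withdrawal is by investigator decision or at the subject's request. The rule does not distinguish a child who withdraws before receiving the monitor from one who withdraws after a failed night or after a good one.
- **Target number (2, Enrollment).** The plan is to enroll 125, "assuming a 20% drop out rate from the study, with an end goal of one hundred study patients". The causes and timing of the dropouts are not given.
- **Primary decision (6.4).** "The study will be defined feasible if 85% or more of participants provide 6 or more hours of analyzable data". *Participants* is not defined further, and no passage says that withdrawn children remain in the count.

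The course of the study also matters. The home study comes first (4.3.1): "All eligible subjects will be asked to conduct an unattended, overnight sleep study performed in their home prior to in-laboratory polysomnography". Families are told that "they may refuse to participate and may withdraw from the study at any time without penalty" (7.3), and 4.7 adds that "the study ends at any time the patient or parent/caregiver requests it to end". A family may also stop the home study without leaving the trial: if the equipment is too uncomfortable or "too challenging for parents to maintain they will be free to remove the device at any time" (7.3). A child whose home study fails stays in: "Regardless of whether a subject successful completes home sleep testing, in-laboratory polysomnography will still be performed" (4.3.1).

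**The concern.** The primary outcome asks whether families can obtain 6 hours of usable data at home. A family that receives the monitor, cannot manage it and withdraws is an instance of the failure the endpoint is meant to record. If that child is replaced and dropped from the count, the failure disappears from the result and another child takes the place.

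Because the home study precedes the laboratory study, the opposite can also happen. A child may record a valid night and withdraw before the laboratory visit, and a success is then lost.

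In both cases the single feasible/not-feasible decision would rest on children who remained in the study. The question the protocol poses is about children sent home with the device.

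**Working it through.** **Inputs.** Target 100, enrolment 125 and dropout 20% (section 2). Threshold 85% (6.4). Cited success rates of 91% on the first attempt, 98% after one repeat, and 93% (4.3.1). The number of children who withdraw after receiving the monitor, and how many of them already have 6 hours of data, are not given. Both are varied below as assumptions.

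**Step 1: the protocol's own figure.** 100 / (1 − 0.20) = 125. This reproduces, so the 100 is the number left after dropouts, and 125 − 100 = 25 is the planned number of dropouts.

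**Step 2: replaced children who all lack 6 hours of data.** With 85 successes among 100 retained (just feasible) and w such replaced children, the rate among all given the monitor is 85 / (100 + w).

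- w = 5: 85/105 = 81.0%
- w = 10: 85/110 = 77.3%
- w = 25: 85/125 = 68.0%. This needs all 25 planned dropouts to have had the monitor and none to have had 6 hours of data.

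**Step 3: a mix.** Suppose all 25 had the monitor and k of them had 6 hours of data. The rate is (85 + k) / 125.

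- k = 21: 106/125 = 84.8%
- k = 22: 107/125 = 85.6%
- k = 25: 110/125 = 88.0%

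The break-even for staying at or above 85% is 22 of 25.

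**Step 4: the downward direction.** With 84/100 retained (not feasible) and w children lost after a valid recording, the rate is (84 + w) / (100 + w). At w = 6 it is 90/106 = 84.9%, and at w = 7 it is 91/107 = 85.05%. Seven such losses would be enough to hide a rate above the threshold.

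**Step 5: margin at the cited rates.** If the cited rates held among the retained 100, the smallest w of replaced failures that takes s / (100 + w) below 85% is:

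- s = 91: w = 8 (91/108 = 84.3%)
- s = 93: w = 10 (93/110 = 84.5%)
- s = 98: w = 16 (98/116 = 84.5%)

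**Step 6: limits over any mix.** Let T be the successes among 125 children given the monitor, with 25 replaced. Successes in the retained 100 lie between max(0, T − 25) and min(100, T).

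| T of 125 | Full rate | Retained 100 |
|---|---|---|
| 84 or fewer | 67.2% or less | never reaches 85; verdict unchanged |
| 85 to 106 | 68.0% to 84.8% | could be called feasible although the full rate is below 85% |
| 107 to 109 | 85.6% to 87.2% | could be called not feasible (minimum 82 to 84) although the full rate is above 85% |
| 110 or more | 88.0% or more | always at least 85; verdict unchanged |

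**The case against.** The strongest reply is that 8.2 is a recruitment rule. It says another child is enrolled and does not define an analysis set. Replacing a child is compatible with keeping that child in the feasibility count, and 6.4 speaks of *participants*, not of completers or of the 100. An analysis plan that is not shown here may settle the denominator. This stands in part: exclusion is an inference, and a reader should not conclude that the protocol states it. What remains is that both rules are fixed in the protocol, replacement is tied to a fixed 100, and nothing there prevents the natural reading.

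Second, the affected group is narrow. Families who take the device off without withdrawing, and children who fail at home but stay, are not replaced under 8.2 and still count as failures. This stands. A reader might infer that every failed home test is replaced, but sections 4.3.1 and 7.3 do not support that. The problem is confined to formal withdrawal.

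Third, the direction is not determined. This also stands. A reader might infer that the rate must be inflated, but withdrawals after a valid recording push the other way, and the 20% dropout has no stated cause or timing.

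Fourth, the cited success rates of 91% to 98% leave a margin. That is reassuring but not conclusive. As reported in 4.3.1, those rates describe successful or interpretable studies, not 6 or more hours of data, and the 93% combines 26 patients studied in hospital with 75 studied at home.

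**Conclusion.** The concern holds in conditional form. Sections 8.2 and 6.4 together allow, and most naturally suggest, a feasibility rate computed on children who stayed. On that reading a monitor-related withdrawal could be replaced instead of counted as a failure, and a success followed by withdrawal could be lost.

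The size is unknown because the protocol does not say how many withdrawals come after the monitor is given. For 5 to 10 replaced failures at the 85/100 boundary, the rate falls to between 81.0% and 77.3%. The 68.0% figure is an outer limit resting on two assumptions that nothing in the protocol supports, and should not be read as an expected value.

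The verdict is at risk mainly when true success is near or below 85%. With 125 given the monitor and 25 replaced, it cannot change at 110/125 (88%) or more, so it is unlikely to change if success is in the range the protocol cites. The point deserves correction because it touches the only primary decision and the remedy is simple. It does not show that a feasible verdict would be wrong.

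**What to change.** - **Section 6.4:** define the primary denominator as every participant given the home monitor, whether or not later withdrawn. Count those with 6 or more hours of analyzable data as successes and all others as failures.
- **Section 8.2:** state that replacement serves only to maintain the number of paired home and laboratory studies for the secondary comparisons, and removes no child from the primary analysis.

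This deals with both directions of bias, since a valid recording made before withdrawal is kept as a success. Children who withdraw before receiving the monitor fall outside the denominator and can be replaced freely.

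The cost is about one sentence in each section, with no extra patients or visits. The reported feasibility rate may be slightly less favourable, and a few withdrawals unrelated to the monitor will count as failures.

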Appendix A: Modified STOP-Bang Tool for Stratifying OSA in Children

Modified from Combs (2015)⁸

- 1) **SNORING:** How often does your child snore loudly? **Don't know, never, rarely, occasionally, frequently, or almost always.**
- 2) **TIRED:** Is your child sleepy during the daytime? **Don't know, never, rarely, occasionally, frequently, or almost always.**
- 3) **OBSERVED APNEA:** Does your child stop breathing during sleep? **Don't know, never, rarely, occasionally, frequently, or almost always.**
- 4) **BLOOD PRESSURE:** Systolic or diastolic blood pressure greater than or equal to 95th percentile for height and age? **Yes or No?**
- 5) **BODY MASS INDEX:** Greater than 95th percentile for age? **Yes or No?**
- 6) **ACADEMIC PROBLEMS:** Does your child have learning problems? **Don't know, never, rarely, occasionally, frequently, or almost always.**
- 7) **NECK SIZE:** Is your child's neck circumference greater than the 95th percentile for age? **Yes or No?**
- 8) **GENDER:** Is your child's **Gender** Male? **Yes or No?**

Answers with choice that include don't know, never, rarely, occasionally, frequently, or almost always are collapsed into a positive or negative response in the following manner:

- 1) Frequently or almost always is considered a positive response.
- 2) Don't know, never, rarely, or occasionally are considered a negative response.
